10.4 Secondary Patient-reported Outcomes

The following scales will be used for targeted patient-reported outcomes:

- 1.) Change in perceived social isolation (Likert 1-5 scale: Never, Rarely, Sometimes, Often, Always)
 - a. I feel left out.
 - b. I feel that people barely know me.
 - c. I feel isolated from others.
 - d. I feel that people are around me but not with me.
- 2.) Change in perceived self-efficacy (i.e., "How confident are you that you can stick with healthful foods?" Likert 1-10 scale: ranging from Not Confident to Completely Confident)
 - a. Even if you need a long time to develop necessary routines?
 - b. Even if you have to try several times to make it work?
 - c. Even if you have to rethink your entire way of nutrition?
 - d. Even if you have to make a detailed plan?
- 3.) Change in perceived caring (i.e., "My current meals help to create a caring environment that helps me heal": Likert 1-5 scale: Strongly Disagree, Disagree, Neither Agree nor Disagree, Agree, Strongly Agree)

Responses to survey questions will be collected at baseline by phone and at the 10week follow-up phone call conducted by KPNC DOR research staff.

11 Supporting Documentation and Operational Considerations

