### 3 General analysis considerations

### 3.1 Analysis populations

**Primary analysis population**: The primary analysis population will consist of all patients who are randomized and consented to the KP NOURISH study and who survive until hospital discharge, divided into those assigned to MTMs (in addition to Usual Care) and those assigned to receive Usual Care alone. Participants will be analyzed as randomized according to the intention-to-treat principle, regardless of receipt of MTMs.

**Heart failure subpopulation:** The heart failure subpopulation will include all patients in the primary analysis population with pre-existing heart failure as their qualifying medical condition. This population will be analyzed as randomized (MTMs vs. Usual Care) according to the intention-to-treat principle.

**Diabetes subpopulation:** The diabetes subpopulation will include all patients in the primary analysis population with pre-existing diabetes mellitus as their qualifying medical condition. This population will be analyzed as randomized (MTMs vs. Usual Care) according to the intention-to-treat principle.

**Patient reported outcomes subpopulation:** The patient reported outcomes (PRO) subpopulation will include all participants in the primary analysis population with complete baseline and follow-up surveys and excludes participants who died or did not complete the follow-up survey. This population will be analyzed as randomized (MTMs vs. Usual Care) according to the intention to treat principle.

**MTMs subpopulation:** The MTMs subpopulation will include all patients in the primary analysis population who are randomized to either MTMs alone or MTMs with remotely delivered nutritional counseling. This population will be analyzed as randomized (MTMs alone vs MTMs with remotely delivered nutritional counseling) according to the intention-to-treat principle.

**Heart failure MTMs subpopulation:** The heart failure MTMs subpopulation will include all patients with pre-existing heart failure as their qualifying medical condition who are randomized to either MTMs alone or MTMs with remotely delivered nutritional counseling. This population will be analyzed as randomized (MTMs alone vs MTMs with remotely delivered nutritional counseling) according to the intention-to-treat principle.

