#### 3.3 Covariates

Baseline characteristics overall and by treatment arm will be described using the list of covariates in **Table 3-1**. Balance of characteristics will be assessed using standardized differences. Given the potential unknown impact of one or more surges of Covid-19 during the enrollment and follow-up period of the study, an *a priori* decision was made to adjust for indices for acute severity of illness, predicted short-term readmission risk and multimorbidity burden as well as the presence of active Covid-19 during the index hospitalization, along with any observed additional baseline differences in participant characteristics for regression models of efficacy.

**Table 3-1.** List of candidate covariates.

| Category                              | Variables   |
|---------------------------------------|---|
| Demographic characteristics           | Age, self-reported gender, self-reported race/ethnicity   |
| Prior medical history                 | Heart failure, diabetes mellitus, chronic kidney disease, acute myocardial infarction, coronary artery bypass surgery, percutaneous coronary intervention, mitral or aortic valvular disease, atrial fibrillation or flutter, ventricular tachycardia or fibrillation, ischemic stroke or transient ischemic attack, venous thromboembolism, hypertension, dyslipidemia, current smoker, hospitalized bleed, hyperthyroidism, hypothyroidism, chronic liver disease, chronic lung disease, diagnosed depression, diagnosed dementia |
| Pre-admission vital signs             | Body mass index, systolic blood pressure  |
| Index hospitalization characteristics | length of stay, major discharge diagnosis category (MDC) based on diagnosis-related groups (DRG), laboratory-based acute physiology score version 2.0 (LAPS 2), predicted readmission risk score, comorbidity point score version 2.5 (COPS 2.5), evidence of active Covid-19 infection   |
| Inpatient laboratory values           | Hemoglobin, serum creatinine, blood urea nitrogen   |

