### 3.4 Missing data

The state-of-the-art EHR at KPNC will be used to identify all hospitalizations and emergency department visits, including any that occur at non-network hospitals given that KPNC is fiscally liable for these types of urgent or emergent resource utilization. Deaths are systematically captured through EHR data (including participant proxy reporting) complemented by external state death certificate data and Social Security Administration vital status file information, with >97% estimated capture based on prior studies involving KPNC members. In addition, all participants' medical records will be manually reviewed for the occurrence of death at the end of follow-up if the research team is unable to reach the participant or their listed secondary contact(s). Thus, it is unlikely to be missing data on clinical outcomes or that data availability will be differentially available between those assigned to MTMs or Usual Care. Participants with missing data from follow-up surveys will be excluded from analyses of patient-reported outcomes.

Missing data on covariates will be described in the baseline table and imputed for use in models, as needed. If less than 5% of covariate data are missing across all covariates of interest, then missing data will be imputed using the median value of each covariate in the full sample. If more than 5% of data are collectively missing for covariates of interest, then a multiple imputation approach will be used to impute data across all covariates.

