#### 4.3 Secondary patient-reported outcomes

The following scales will be analyzed for the targeted patient-reported outcomes:

- 1.) Change in perceived social isolation (Likert 1-5 scale: Never, Rarely, Sometimes, Often, Always)
  - a. I feel left out.
  - b. I feel that people barely know me.
  - c. I feel isolated from others.
  - d. I feel that people are around me but not with me.
- 2.) Change in perceived self-efficacy (i.e., "How confident are you that you can stick with healthful foods?" Likert 1-10 scale: ranging from Not Confident to Completely Confident)
  - a. Even if you need a long time to develop necessary routines?
  - b. Even if you have to try several times to make it work?
  - c. Even if you have to rethink your entire way of nutrition?
  - d. Even if you have to make a detailed plan?

3.) Change in perceived caring (i.e., "My current meals help to create a caring environment that helps me heal": Likert 1-5 scale: Strongly Disagree, Disagree, Neither Agree nor Disagree, Agree, Strongly Agree)

All answers to survey questions will be reported at baseline and follow-up in the PRO subpopulation. The change in responses to each survey question will be measured as the difference in score between follow-up and baseline responses. The proportion of participants with a decrease in isolation, increase in self-efficacy, or increase in perceived caring responses from baseline to follow-up will also be reported and compared using chi-squared tests.

A difference-in-differences approach will be used to compare the change in each survey question response by assigned group. The measure of association will be the coefficient (95% CI) for MTMs vs. Usual Care in linear regression models for each change in response adjusted for baseline differences in the PRO subpopulation.

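### The patient-reported outcome models do not prespecify each item's own baseline score, and complete-responder sets are labelled intention-to-treat

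*SAP*

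**What the plan says.** The items are asked twice. Protocol 10.4: "Responses to survey questions will be collected at baseline by phone and at the 10week follow-up phone call". There are nine: four on social isolation, four on self-efficacy and one on perceived caring.

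SAP 4.3 defines the outcome: "The change in responses to each survey question will be measured as the difference in score between follow-up and baseline responses". It then states: "A difference-in-differences approach will be used to compare the change in each survey question response by assigned group". The effect measure is the treatment coefficient from "linear regression models for each change in response adjusted for baseline differences in the PRO subpopulation". SAP 4.4 repeats this for MTMs alone against MTMs with counseling.

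SAP 3.3 fixes adjustment for acute severity, predicted readmission risk, multimorbidity and active Covid-19, "along with any observed additional baseline differences in participant characteristics for regression models of efficacy". Table 3-1, the candidate list, contains no patient-reported item and does not list medical center, although Protocol 7.4 stratifies randomisation by center.

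On who is analysed, the patient-reported outcome set in SAP 3.1 requires complete baseline and follow-up surveys and "excludes participants who died or did not complete the follow-up survey". SAP 3.4 adds: "Participants with missing data from follow-up surveys will be excluded from analyses of patient-reported outcomes". Imputation is planned for covariates only. SAP 3.1 nevertheless describes this set, and the matching set for the two MTMs arms, as analysed under the intention-to-treat principle. No sensitivity analysis for missing surveys is given.

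**The concern.** There are two separate faults.

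The first concerns precision. A change score in effect fixes the slope on the baseline score at 1. ANCOVA estimates that slope, and in a randomised comparison it has smaller variance unless the correlation is 1. The baseline answers are already collected, so leaving their use to an observed imbalance gives up precision and makes the model depend on the data.

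The second concerns who is compared. Survival to the survey and answering it both happen after randomisation, so a set chosen on them is not the full randomised comparison. Response could differ by arm. MTMs participants have weekly delivery contact (Protocol 8.2.1), while usual care is followed passively (8.1). The gift card is described only for usual care (6 and 8.3). The survey is triggered by the last delivery in the MTMs arms and by 10 weeks from discharge in usual care (8.3).

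Aim 3 and the patient-reported part of Aim 4 are at stake.

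**Working it through.** **Inputs from the documents.** 1000 vs 1000 and 500 vs 500, two-sided α = 0.05, more than 80% power for small differences (SAP 2); change score per item (SAP 4.3).

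**Not in the documents, so assumed or varied.** Raw-score SD (set to 1, equal at both times), size of a small difference (0.2 SD), correlation ρ (0 to 0.9), and response rates.

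**Step 1: the plan's own power statement.** Detectable difference at 80% power = (1.960 + 0.842) × √(2/n), in SDs of the analysed variable.
- n = 1000 per arm: 0.125 SD. n = 500 per arm: 0.177 SD.
- Power at 0.2 SD: 99.4% and 88.5%. At 0.1 SD: 60.9% and 35.2%.

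The statement gives no effect size or SD, so it cannot be strictly reproduced. It is consistent if small means 0.2 SD and everyone responds. With 500 per arm and 0.2 SD, assumed non-response of 20% or 30% lowers power to 80.7% or 75.4%.

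**Step 2: change score against ANCOVA.**
- Variance of the change score: 2(1−ρ).
- Residual variance with the baseline score as covariate: 1−ρ².
- Ratio: (1−ρ²) / [2(1−ρ)] = (1+ρ)/2.

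The table shows change score / ANCOVA, in raw-score SDs.

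| ρ | Variance | Ratio | Detectable, 1000 per arm | Detectable, 500 per arm | Power for 0.2 SD, 500 per arm |
|---|---|---|---|---|---|
| 0.3 | 1.40 / 0.91 | 0.65 | 0.148 / 0.120 | 0.210 / 0.169 | 76.2% / 91.2% |
| 0.5 | 1.00 / 0.75 | 0.75 | 0.125 / 0.109 | 0.177 / 0.153 | 88.5% / 95.5% |
| 0.7 | 0.60 / 0.51 | 0.85 | 0.097 / 0.089 | 0.137 / 0.127 | 98.3% / 99.3% |

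Example, ρ = 0.3 and 500 per arm:
- Change score: SE = √(1.40 × 2/500) = 0.0748; 0.2/0.0748 − 1.960 = 0.713; power 76.2%.
- ANCOVA: SE = √(0.91 × 2/500) = 0.0603; 0.2/0.0603 − 1.960 ≈ 1.355; power 91.2%.

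The change score falls below 80% power at 500 per arm when 2(1−ρ) exceeds (0.2/2.802)² × 250 = 1.274, that is, when ρ is below about 0.36. With 1000 per arm, power at 0.2 SD is 88.5% even at ρ = 0.

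**Step 3: what selective response can do.** A null-effect simulation used 2,000,000 patients per scenario and about 80% response overall. Response depended on the score in one arm only. Bias in SDs at ρ = 0.3, 0.5, 0.7:

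| Response depends on | Complete-case change score | Complete-case ANCOVA |
|---|---|---|
| Baseline score | −0.068, −0.048, −0.031 | 0.001, 0.002, −0.001 |
| Follow-up score | +0.070, +0.051, +0.032 | +0.093, +0.077, +0.053 |

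The baseline covariate removes the first kind of bias but not the second, where ANCOVA is somewhat worse. The two faults therefore need separate remedies. The signs follow from the scenario chosen and predict nothing about this trial.

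**The case against.** The strongest defence is that the SAP does not exclude the baseline score. Its phrase on baseline differences sits in a section about baseline and follow-up answers and could cover it. Section 4.3 also falls under the efficacy heading, so the four indices fixed in SAP 3.3 may already apply. That stands. A reader might infer that the models are unadjusted or omit the baseline score outright; the text does not say so. What remains is that the score is not prespecified, and none of the four indices is a patient-reported item.

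A reader might also infer a low correlation because baseline is taken in the hospital room, where current meals may mean hospital meals. That wording appears only in the caring item, so the argument does not reach the other eight.

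Regression to the mean is not an additional harm. Chance imbalance is the source of the extra variance: 2(1−ρ) − (1−ρ²) = (1−ρ)². With 1000 per arm, typical imbalance is √(2/1000) = 0.045 SD, of which (1−0.5) × 0.045 = 0.022 SD carries into the change score at ρ = 0.5.

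On the label, the SAP defines its set openly and keeps participants in their assigned arms. That is fair, but intention-to-treat also concerns who is included. Whether one unanswered item removes a participant is unclear from the text.

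Finally, weekly contact might raise response in the MTMs arms and the gift card might raise it in usual care. The documents do not support inferring that the results will be biased towards MTMs, or by any particular amount.

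**Conclusion.** The point holds as a worthwhile improvement to secondary analyses. With full response, and baseline answers unaffected by the arm already assigned, the planned estimate is unbiased but less precise than ANCOVA for every correlation below 1. Over assumed correlations of 0.3 to 0.7, ANCOVA needs 65% to 85% of the change-score variance. This is modest for MTMs vs usual care and matters mainly for MTMs alone vs MTMs with counseling, and there mainly at low correlation. These sizes assume equal variances at both times.

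The intention-to-treat label is wrong for sets selected on survival and response after randomisation. Arm-related response bias is possible; its size and direction cannot be derived from the documents. The clinical outcomes, including those within Aim 4, and the primary readmission analysis do not depend on any of this.

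**What to change.** 1. In every patient-reported outcome model in SAP 4.3 and 4.4, include that item's baseline score and medical center as fixed covariates, whether or not an imbalance is seen. The outcome can stay a change score: once the baseline score is in the model, the treatment coefficient is the same for the change and for the follow-up score.
2. In SAP 3.1, describe both patient-reported outcome sets as complete cases analysed as randomised, and say whether one unanswered item removes a participant from all models or only from that item's model.
3. Report survey response and deaths by arm.
4. Add a sensitivity analysis among week-10 survivors using multiple imputation by arm, with baseline scores, covariates and EHR readmission and emergency department status.

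The first change is free, since the scores are already collected. The rest costs SAP wording and modest programming. SAP 3.4 plans multiple imputation for covariates only, and only above 5% missing, so the outcome imputation is new work. It assumes data are missing at random, does not cure response that depends on the week-10 answer itself, and still conditions on survival. It therefore belongs as a sensitivity analysis beside the complete-case result; making it the main analysis would be debatable.

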#### 4.4 Secondary comparisons

All outcome comparisons outlined in Sections 4.1 – 4.3 will be repeated in the MTMs, heart failure MTMs, diabetes MTMs, and PRO MTMs subpopulations, as appropriate. Frequencies and risks, risk differences, hazard ratios, subdistribution hazard ratios, and linear regression coefficients will be calculated and reported comparing participants assigned to MTMs alone versus assigned to MTMs with remotely delivered nutritional counseling.
